9.5.1 Estimated Distribution of Follow-up

Table 5 and Table 6 show the estimated distribution of follow-up of users of tacrolimus assuming a 4-year extension (2002-2015) with a period of inclusion of new users from the date of first availability of topical tacrolimus and topical pimecrolimus in each study population through December 31, 2014, and a follow-up of all new users through December 31, 2015. Numbers are presented for children aged 0 to less than 18 years (Table 5) and adults aged 18 years or older (Table 6). Overall, it is estimated that approximately 14,000 children and 59,000 adults will be followed for at least 5 years.

Table 5. Estimated Number of Users by Years of Follow-up, Among New Users of Tacrolimus, Children Aged Less Than 18 Years; JOELLE Extension (2002-2015)

Years of Follow-up	Number of Users by Years of Follow-up		Cumulative Number of Users by Years of Follow-up	
	n	(%)	n	(%)
< 1	254	(1)	25,479	(100)
1 to < 2	2,345	(9)	25,225	(99)
2 to < 3	2,584	(10)	22,880	(90)
3 to < 4	2,903	(11)	20,296	(80)
4 to < 5	3,146	(12)	17,393	(68)
5 to < 6	3,115	(12)	14,247	(56)
6 to < 7	2,784	(11)	11,132	(44)
7 to < 8	2,098	(8)	8,348	(33)
8 to < 9	2,338	(9)	6,250	(25)
9 to < 10	2,144	(8)	3,912	(15)
10 to < 11	618	(2)	1,768	(7)
11 to < 12	578	(2)	1,150	(5)
12 to < 13	464	(2)	572	(2)
13 to < 14	108	(0)	108	(0)

Table 6. Estimated Number of Users by Years of Follow-up, Among New Users of Tacrolimus, Adults Aged 18 Years or Older; JOELLE Extension (2002-2015)

Years of Follow-up	Number of Users by Years of Follow-up		Cumulative Number of Users by Years of Follow-up	
	n	(%)	n	(%)
< 1	1,032	(1)	103,175	(100)
1 to < 2	9,640	(9)	102,143	(99)
2 to < 3	10,100	(10)	92,503	(90)
3 to < 4	11,020	(11)	82,403	(80)
4 to < 5	11,527	(11)	71,383	(69)
5 to < 6	11,386	(11)	59,856	(58)
6 to < 7	10,947	(11)	48,470	(47)
7 to < 8	9,729	(9)	37,523	(36)
8 to < 9	10,582	(10)	27,794	(27)
9 to < 10	10,956	(11)	17,212	(17)
10 to < 11	2,353	(2)	6,256	(6)
11 to < 12	2,168	(2)	3,903	(4)
12 to < 13	1,550	(2)	1,735	(2)
13 to < 14	185	(0)	185	(0)

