9.5 Study Size

We have updated the study size calculations for conducting the JOELLE Extension based on the incidence rates of each malignancy observed in Phase I and the updated annual number of users of tacrolimus in each data source. Calculations assume an extension of 4 years (through December 31, 2015), with a period of 3 years of inclusion of users and 1 year of follow-up. This ensures all users are followed for at least 6 months after applying a 6-month induction period. The total number of users in Phase I and the estimated number of users in the JOELLE Extension and the corresponding person-years of follow-up are presented in Table 3. In some databases, data beyond 2015 may be available and will be included in the study.

Table 3. Number of New Users of Tacrolimus and Person-years of Follow-up in Phase I (2002–2011) and Estimated Number in the JOELLE Extension (2002-2015)

	Phase I ^a		Extension ^b	
	Number of New Users	Person-years of Follow-up	Estimated Number of New Users	Estimated Person-years of Follow-up
Children aged < 18 years	19,948	50,316	24,412	133,285
Adults aged ≥ 18 years	66,127	198,400	98,788	551,369

^a Actual values.

^b Based on a 4-year extension (additional 3-year period of inclusion plus 1 year of follow-up) accounting for 6-month induction period.

In Table 4, we present the probability for each study endpoint to have an upper limit for the two-sided 95% CI of the rate ratio below the specific values of 2, 4, 8, and 16, according to the estimated number of users of tacrolimus, assuming a 4-year extension (additional 3-year period of inclusion plus 1 year of follow-up) and the incidence rates observed in Phase I.

For the pediatric population, the probabilities, although higher than in Phase I, are still low. The highest probability is for any lymphoma, with a 70% probability for having an upper limit of the 95% CI of the rate ratio below 8.

For the adult population, probabilities, already high in Phase I, have increased for the JOELLE Extension. The probability is 95% or higher for having an upper limit of the 95% CI of the rate ratio below 2 for NMSC, melanoma of skin, and non-Hodgkin lymphoma. For Hodgkin lymphoma and CTCL, the probabilities are 95% and 85%, respectively, for having an upper limit below 4.

Table 4. For Each Study Outcome, Probability That the Upper Limit of the 95% Confidence Interval of the Incidence Ratio is Below 2, 4, 8, or 16; JOELLE Extension (2002-2015)

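### Table 3 prints person-years that belong to the larger user counts of Tables 5 and 6, and the adult counts agree with Phase I only on a basis that the protocol does not state

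*Protocol*

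**What the plan says.** Section 9.5 states that "the estimated number of users in the JOELLE Extension and the corresponding person-years of follow-up are presented in Table 3". The rows of Table 3 give Phase I users, Phase I person-years, extension users and extension person-years, in that order: "Children aged < 18 years 19,948 50,316 24,412 133,285" and "Adults aged ≥ 18 years 66,127 198,400 98,788 551,369". The Phase I columns carry the footnote "a Actual values". The extension columns are footnoted "Based on a 4-year extension (additional 3-year period of inclusion plus 1 year of follow-up) accounting for 6-month induction period". Section 9.5 says that the calculations use "the updated annual number of users of tacrolimus in each data source". Table Abstract-1 repeats all eight figures.

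Section 9.5.1 introduces its two tables with "Table 5 and Table 6 show the estimated distribution of follow-up of users of tacrolimus assuming a 4-year extension (2002-2015", with inclusion of new users through the end of 2014 and "a follow-up of all new users through December 31, 2015". The top of the cumulative column is 25,479 in Table 5 (children) and 103,175 in Table 6 (adults). No text relates these totals to Table 3.

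**The concern.** Both sections describe new users of tacrolimus under one 4-year extension with the same inclusion and follow-up dates, so each age group should have one user count, and the person-years should be those of that count. Neither holds on the printed figures. In addition, an adult with 4 years of follow-up at 31 December 2015 must have started by 31 December 2011, the end of Phase I, so the number of such adults can be checked against the Phase I count.

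At stake is the stated size of the extension: the headline figures in the abstract, the basis that Section 9.5 gives for Table 4, and the statement in Section 9.5.1 on how many users will be followed for at least 5 years.

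**Working it through.** Inputs: the Table 3 figures quoted above, and the rows of Tables 5 and 6. Write n(k) for the number of users with k to under k+1 years of follow-up, k = 0 to 13.

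1. **Plan's person-years reproduced.** Give each user the row midpoint, k + 0.5, and deduct 0.5 year for the induction period.
   - Children: 146,020.5 − 0.5 × 25,479 = 133,281 (Table 3: 133,285).
   - Adults: 602,953.5 − 0.5 × 103,175 = 551,366 (Table 3: 551,369).
   - Without the deduction, the sums are 9.6% and 9.4% too high. With the midpoints scaled to Table 3's user counts and no deduction, they are 139,906 and 577,316, still 5.0% and 4.7% too high. Of the variants tried, only the full Table 5 and 6 cohorts less six months match.

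2. **User counts.** The rows sum to the printed totals and the cumulative columns are internally correct.
   - Children: 25,479 − 24,412 = 1,067 (+4.4%).
   - Adults: 103,175 − 98,788 = 4,387 (+4.4%).

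3. **Can users lost to the 6-month lag explain the gap?** Only users with under 1 year of follow-up could have no time left after the lag. There are 254 children and 1,032 adults in those rows, about a quarter of each gap.

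4. **Person-years that would go with Table 3's counts**, follow-up distribution unchanged:
   - Children: 133,285 × 24,412 / 25,479 = 127,703.
   - Adults: 551,369 × 98,788 / 103,175 = 527,925.
   - Both are about 4.2% below the printed values.

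5. **Users with at least 4 years against Phase I.**
   - Adults: 71,383 against 66,127, an excess of 5,256 (+7.9%).
   - Children: 17,393 against 19,948, no excess.
   - Both groups together: 88,776 against 86,075, an excess of 2,701, so moving users between age groups cannot by itself account for the adult figure.

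6. **Adult person-years against a ceiling with no attrition.** Assume that the Phase I person-years are already net of the lag, that every Phase I adult contributes 4 further years, and that accrual in 2012–2014 is even. Mean follow-up of later entrants to the end of 2015 is then 2.5 years, or 2.0 after the lag.
   - 198,400 + 4 × 66,127 + (98,788 − 66,127) × 2.0 = 528,230. The stated 551,369 is 4.4% above it.
   - Now suppose that the Phase I count omits the 5,256 adults needed to reconcile step 5, all starting in the second half of 2011. Their lag ends on average about a quarter of the way into 2012, leaving 3.75 years each: 528,230 + 5,256 × 3.75 = 547,940. The excess is 0.6%.
   - Children, first method: 50,316 + 4 × 19,948 + 4,464 × 2.0 = 139,036, above the stated 133,285, so there is no excess.

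7. **Sensitivity of precision.** Take adult Hodgkin lymphoma (4.4 per 100,000), a true rate ratio of 1, an assumed 4:1 comparator ratio and a normal approximation. The chance of an upper limit below 2 is Φ(ln 2 / √(1.25/E) − 1.96), where E is the expected number of exposed cases. With 551,369 person-years, E = 24.26 and the chance is 0.863; with 527,925, E = 23.23 and it is 0.848. Neither equals the 0.43 printed in Table 4. Which inputs produced Table 4 is a separate question; the comparison here shows only how little a 4% change matters.

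**The case against.** The strongest reply is that the tables may be counted on different bases. The abstract describes the Phase I figures as patients studied, the analysis discards the first 6 months of person-time, and non-overlapping propensity scores are trimmed. If the Phase I count leaves out adults who started after mid-2011 and had no time after the lag, roughly half of Table 6's band of 4 to under 5 years is missing from it: 11,527 / 2 ≈ 5,764. Then 66,127 + 5,764 = 71,891, just above 71,383, and the conflict in step 5 goes away. Table 3's extension counts also exceed Phase I by amounts that are whole multiples of three (3 × 10,887 adults, 3 × 1,488 children), as if three equal annual intakes had been added to the Phase I count. Half a year's intake is then 5,444 adults and 744 children, against gaps of 4,387 and 1,067: a rough fit overall, a poorer one by age group.

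This stands as a possible explanation, and it limits what can be concluded. A reader might infer that Table 6 contains an outright impossible number of adults, or that the adult person-years are at least 4% above any attainable value. The document supports neither, because the counting basis of Phase I is not given. A reader might also infer that the projection ignores death and disenrolment altogether. Table 6 does not bear that out: entry closes a year before follow-up ends, so the 1,032 adults with under 1 year must have left early.

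The explanation does not remove the mismatch between users and person-years. If the bases differ, Table 3 sets a count on one basis beside person-years on another and calls them corresponding. It is also true that this is a database study in which every eligible user enters whatever Table 3 says, so the error does not alter who is studied.

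**Conclusion.** The contradiction between Table 3 and Tables 5 and 6 is firm and rests on printed figures alone: user counts 4.4% apart in both age groups, and person-years that belong to the larger counts. Which set is right cannot be told from the protocol. If Table 3's counts are right, the person-years should be about 4% lower.

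The comparison of Table 6 with Phase I is conditional. As printed, the adult figures conflict; they can be reconciled only on a counting basis that the protocol does not state. The adult person-years imply little attrition relative to Phase I, but by an amount that cannot be fixed: about 0.6% to about 4% above a ceiling with no attrition, under the accrual assumptions shown, and slightly less than 0.6% if more late starters were omitted than the minimum needed. Neither this nor the conflict over 4 years of follow-up arises for children.

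The effect on precision is small (about 0.86 to 0.85 in the example, at an assumed 4:1 ratio) and no conclusion of Section 9.5 is shown to reverse. This should be corrected because these are the stated size figures of the extension, not because it threatens the study.

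**What to change.** Put Tables 3, 5 and 6 and Table Abstract-1 on one counting basis, with one user count per age group and the person-years that belong to it. State in a footnote whether the Phase I and extension counts are taken before or after the 6-month lag and any propensity-score trimming, so that Table 6 can be checked against Phase I. Recompute Table 4 from the reconciled person-years, and carry any change into the statement in Section 9.5.1 on users followed for at least 5 years.

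The cost is a recalculation from figures already held. If Table 3's counts are kept, person-years fall by about 4% and the projection looks slightly less favourable. If the larger counts are kept, the person-years stand and the counts in Table 3 and the abstract change.

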9.6 Data Collection

Routine procedures include checking electronic files, maintaining security and data confidentiality, following analysis plans, and performing quality-control checks of all programs. Each database research partner will maintain any patient-identifying information securely onsite according to internal standard operating procedures.

Security processes will be in place to ensure the safety of all systems and data. Every effort will be made to ensure that data are kept secure so that they cannot be accessed by anyone except select study staff.

Appropriate data storage and archiving procedures will be followed (i.e., storage on CD-ROM and DVD), with periodic backup of files to tape. Standard procedures will be in place at each location handling the data to restore files in the event of a hardware or software failure.

9.7 Data Analysis

This analysis section provides an overview of the analyses that were conducted for this study during Phase I and will be repeated for the JOELLE Extension (final analysis) except when indicated otherwise.

Data analyses will occur in two stages: (1) a country-specific analysis by each of the database research partners and (2) a pooled analysis conducted by the coordinating center, after combining stratified data from each database. The database research partners have organization-specific restrictions on the level and type of information that can be shared externally. This two-stage analysis is designed to meet those restrictions while nevertheless accomplishing the goal of assimilating the data from the collaborating database research partners into one summary analysis. The basic approach is for each database research partner to create stratified tables with cross-classifications of patient and person-time counts by exposure category, endpoint, deciles of propensity scores, and type of prescriber. To estimate overall measures of effect, the coordinating center will analyze these stratified data using Mantel-Haenszel methods.

For the JOELLE extension, because of data confidentiality requirements, data from Denmark cannot be shared outside the country. Therefore, stratified data from all databases will be centralized on the servers of Statistics Denmark through the University of Southern Denmark, and the coordinating center will conduct the pooled analysis remotely within these servers.

A common statistical analysis plan will be developed separately and will describe methods for the creation of the study cohorts, the descriptive analyses, variable creation including propensity scores, and the incidence rate and rate ratio analyses. The statistical analysis plan will also detail the required input data from the individual database research partner that will be used to perform the pooled analysis. Calculation of person-years, incidence and rate ratios, and confidence intervals will be documented. A description of the planned pooled analyses and table shells will be included. Appendices to the analysis plan will document all diagnostic, procedure, and medication codes to be used in defining the outcomes, exposures, and covariates. The core statistical analysis plan will be adapted to the specifications of each database.

9.7.1 Country-Specific Analysis

Each database research partner will conduct country-specific analyses to (1) describe the study cohorts at the start date; (2) describe the characteristics of cases; and (3) estimate exposure propensity scores within its data, conduct frequency matching of the tacrolimus and pimecrolimus cohort with the corticosteroids cohorts across strata of propensity scores, and create a summary data set based on counts of patients, person-years, and outcome events according to the strata of propensity scores.

9.7.1.1 Description of the Study Cohorts

Each database research partner will first apply the study inclusion/exclusion criteria to select the study population. During this process, each database research partner will create a patient flow diagram showing the impact that each step of applying the study criteria had on the study size. Once the study population is identified, members of each study cohort (tacrolimus cohort, pimecrolimus cohort, two corticosteroids cohorts, and untreated cohort) will be described as of the start date, with separate analyses performed for children (0 to < 18 years) and adults (\geq 18 years) according to the variables detailed below. In addition, each study cohort will be described for children aged \geq 2 to < 16 years.

Variables for Description of Study Cohort

Variables for the description of the study cohort are those included in Annex 5 for the estimation of propensity scores. In addition, the following variables will be described:

- Duration of available history in the database up to the start date in years: mean (SD), median (P25, P75), and frequency distribution of duration of medical history (for endpoint, use date of first endpoint): \leq 1, 2-4, 5+
- Duration of follow-up in years: mean (SD), median (P25, P75), and frequency distribution of duration of follow-up (for endpoint, use date of first endpoint): \leq 1, 2-4, 5+
- Number of years since first recorded diagnosis of atopic dermatitis: Mean (SD); median (P25, P75); and frequency distribution: \leq 1, 2-4, 5-9, 10-14, 15+
- Number of years since first prescription of topical corticosteroids of any potency plain or combined: Mean (SD); median (P25, P75); and frequency distribution: \leq 1, 2-4, 5-9, 10-14, 15+
- Total number of prescriptions for topical corticosteroids in the 12 months before the start date: 0, 1, 2-3, 4+
 - Topical corticosteroids, plain
 - Weak
 - Moderately potent
 - Potent
 - Very potent

- Topical corticosteroids, combinations with other agents
 - Weak
 - Moderately potent
 - Potent
 - Very potent

9.7.1.2 Description of Patterns of Use

Patterns of use of topical tacrolimus, topical pimecrolimus, and topical corticosteroids during follow-up will also be described for all users included in the study. The analysis of patterns of use will include the total number of prescriptions received, the distribution of prescriptions, and the distribution of total number of grams of active substance per person.

9.7.1.3 Description of Cases

Characteristics of cases at the time of diagnosis will be described for each study endpoint. Characteristics will include age, sex, cancer subtype (e.g., type of NMSC, type of lymphoma), stage of cancer if available, medication exposure category, and selected medical history.

9.7.1.4 Estimation of Propensity Scores

Estimation of propensity scores will be conducted separately for children and adults. For each age group, each database research partner will estimate two separate sets of propensity scores, one set for the analyses comparing users of tacrolimus with users of corticosteroids and another set for the analyses comparing users of pimecrolimus with users of corticosteroids.

The propensity scores, which are based on the values of the covariates at treatment initiation, will estimate the probability that each patient is prescribed the study drug (tacrolimus or pimecrolimus) rather than moderate- to high-potency topical corticosteroids. The propensity score will serve as a within-database variable that summarizes the confounding from a large set of variables. Propensity scores will be estimated using multiple logistic regression models. Covariates to be used for the estimation of propensity scores are those related to the probability of receiving treatment with tacrolimus or pimecrolimus and those associated with the risk of skin cancer and lymphoma. Covariates are measured before initiating treatment with the study medications. A list of covariates to be evaluated is presented in Annex 5. Selection of variables will be conducted using a high-dimensional propensity score algorithm [21]. This algorithm has been shown to perform well in the Danish databases [22]. Patients who contribute follow-up time to both the corticosteroids cohort and one of the exposed cohorts (tacrolimus or pimecrolimus) will be included twice in the model used to estimate propensity scores—once in the corticosteroids cohort, using covariate data values at the time of initiating corticosteroids, and once in the tacrolimus or pimecrolimus cohorts, using covariate data values at the time of initiating tacrolimus or pimecrolimus.

From the fitted propensity score model, a propensity score will be estimated for each patient (twice for any patient who contributes follow-up time to both a study drug cohort and the corticosteroids cohort). The database research partners will categorize exposure

propensity scores in 20 strata (twentiles). Trimming (excluding) nonoverlapping regions of propensity scores will be performed prior to any propensity score implementation.

After trimming, strata of propensity scores will be used to frequency match users of corticosteroids with users of tacrolimus and pimecrolimus. A matching ratio up to 4:1 (corticosteroids to tacrolimus or pimecrolimus), depending on available matches, will be used across strata.

In the JOELLE Extension, the patient characteristics will be described for the study cohorts before and after matching. This will allow the investigators to evaluate the efficiency of the frequency matching conducted. In addition, the baseline characteristics of patients excluded after trimming will be also described to identify subgroups (e.g. more severe patients) for whom the results of the study cannot be generalized.

The strata of propensity scores will be used to stratify person-time of follow-up and number of events for each defined exposure category. This will allow investigators to conduct a stratified analysis with aggregated data from each data source. Mantel-Haenszel methods for stratified data will be used to estimate pooled measures of effect. Additional stratification by type of prescriber of first prescription as a proxy for severity of atopic dermatitis was conducted in PHARMO and Sweden in Phase I and will be conducted in PHARMO, Sweden, and Denmark in the JOELLE Extension, the study data sources where this variable is available. Initially, the propensity scores and counts will be summarized into deciles by combining data from contiguous strata; if this results in cell counts that are too small, some deciles may be further combined, resulting in fewer strata.

Each database research partner will apply the study definitions to calculate person-time of exposure and number of events associated with each exposure category and endpoint definition. Using these data in conjunction with propensity scores, each database research partner will create an exposure summary table containing the essential data for measuring the effect of exposure on the study outcomes while adhering to the restrictions that are imposed on the release of individual-level data from each site.

